Upon consent and enrollment in the study, relevant subject information will be relayed to the Barnes Jewish Hospital (BJH) Investigational Pharmacy. Prior to proceeding to the operating room for lower extremity amputation, the patients will be randomized 1:1 by the BJH Investigational Pharmacy to either placebo saline infusion (twice daily) or a standard adult intravenous dose of NAC (1200mg twice daily) for 6 days post-amputation during the usual post-operative inpatient extremity off-loading and stump monitoring period. The pharmacy will maintain blinding, with no member of the investigational team having access to the record until the conclusion of the trial.

Early Withdrawal of Subjects

Patients unable to tolerate the administration of the drug will be withdrawn from the study at any point during their hospitalization and will continue to be monitored until their condition stabilizes. Patients unable to participate in the Post-operative Day 0 Non-invasive Laser Assisted Fluorescence Angiography (LAFA) will be withdrawn from the study at that time point and will not receive the investigational product. Subjects for which continuous IV access is not medically indicated during the 6 day study drug administration period may be withdrawn from the study. Patients unable to participate in follow-up appointments will also be withdrawn from the study.

When and How to Withdraw Subjects

Patients unable to tolerate the administration of the drug will be withdrawn from the study trial at any point during their hospitalization. Patients unable to participate in follow-up appointments will also be withdrawn from the study. They will continue to be monitored for adverse events as inpatients for the duration of their hospitalization. Patients unable to participate in the Post-operative Day 0 Non-invasive Laser Assisted Fluorescence Angiography (LAFA) will be withdrawn from the study at that time point and will not receive the investigational product. No further study follow up will be required.

Data Collection and Follow-up for Withdrawn Subjects

Patient data will be collected up until time of withdrawal from the study and pooled into the collective analysis along with all other patients.

Study Drug

Description

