N-acetyl cysteine (NAC) ((2R)-2-acetamido-3-sulfanylpropanoic acid) is an amino acid derivative of L-cysteine, which is a precursor to glutathione and cysteine. Historically, NAC has been used to treat acetaminophen overdose [6], as well as mucous secretions in patients with cystic fibrosis or chronic obstructive pulmonary disease [24].

Pharmacokinetics including the following [24] :

Distribution: The steady-state volume of distribution (V_{dss}) and the protein binding for acetylcysteine were reported to be 0.47 liter/kg and 83%, respectively.

Metabolism: N-acetyl-cysteine may form cysteine, disulfides, and conjugates in vivo (N, N'-diacetylcysteine, N-acetyl cysteine-cysteine, N-acetyl cysteine-glutathione, N-acetyl cysteine-protein, etc). Based on published data, it was reported that after an oral dose of 35S-acetylcysteine, about 22% of total radioactivity was excreted in urine after 24 hours. No metabolites were identified.

Elimination: After a single intravenous dose of N-acetyl cysteine, the plasma concentration of total N-acetyl cysteine declined in a poly-exponential decay manner with a mean terminal half-life (T_{1/2}) of 5.6 hours. The mean clearance (CL) for N-acetyl cysteine was reported to be 0.11 liter/hr/kg and renal CL constituted about 30% of total CL.

Treatment Regimen

Upon study enrollment, patients will be randomized 1:1 by BJH Investigational Pharmacy to either placebo ½ normal saline infusion (twice a day) or a standard adult intravenous dose of NAC (1200mg twice a day) for 6 days post-amputation. The BJH Investigational Pharmacy will perform this with knowledge of the patient's medical record number (MRN), and without knowledge of any pre-existing medical conditions, comorbidities, past medical history, prior interventions, etc. The first infusion will be administered within three hours from leaving the operating room. The second infusion will be a minimum of 6 hours after the first infusion, or at 21:00 in an attempt to be consistent with routine hospital BID dosing times. Patients will receive their scheduled infusions as long as they are hospitalized according to the chart below (Table 1). **If medication is not administered within that window, dose will not be given to not interfere with the rest of the doses.**

Table 1:

Post-operative Day (POD)	Infusion Schedule
POD 0	1. Within 3 hours from the conclusion of the operation 2. Approximately 6 hours after first infusion, or at 21:00 +/- 6 hours

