Medications will be prepared by the research pharmacy and delivered to the treating nurse; study drug will be blinded to the research team and the study participant. The research pharmacy will

maintain documentation of medication procurement and preparation, as well as randomization, dispensing, and accountability logs. All medications will be stored in a secure location within the research pharmacy and maintained under controlled environmental conditions. Unused doses will be returned to the research pharmacy, whereas used or unwanted partially infused doses will be destroyed on the nursing unit per policy.

Study Procedures

Screening for Eligibility

As discussed in 2.c, subjects that meet study inclusion and exclusion criteria, who are undergoing an elective above-knee or below-knee amputation at the Washington University School of Medicine-affiliated BJH, will be included in this pilot clinical trial.

Potential subjects will be screened by reviewing the weekly operative schedule, and via referral from vascular surgery faculty study co-investigators. Prior to the scheduled operation, eligible patients will be approached for informed consent. Informed consent will be obtained by a member of the vascular surgery research team in accordance with institutional regulations, prior to any further actions in the study. After informed consent is obtained, a baseline clinical evaluation will be performed including lower extremity anthropometric evaluation, medical history and vital signs documentation. Per standard clinical procedures, all patients will also be evaluated by preoperative anesthesia services. Subjects may **participate in the study a second time on ipsilateral or contralateral site if all Inclusion /Exclusion is reviewed and verified prior to second surgery. Patient records from an outside hospital or facility may be obtained and used for screening and/or follow up in patient care.**

Schedule of Measurements

A. Non-invasive Laser Assisted Fluorescence Angiography (LAFA)

Location of Procedure:

- Barnes-Jewish Hospital Operating Rooms
- 4400/8300/7400/7500 Inpatient Hospital Units
- Other Hospital Units also housing vascular surgery patients

Time of Data Collection:

- **Postoperative Day 0:** Obtained in the operating room after amputation, but before placement of dressings.
- **Postoperative Day3:** Obtained following dressing removal at bedside in the inpatient hospital unit.

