- **Postoperative Day5:** Obtained at the bedside in the inpatient hospital unless the patient is discharged.

Contraindications to LAFA:

- Patient refusal/inability to precipitate in measurement before or during data collection.

- Allergic reaction previously documented to Indocyanine green (ICG) fluorescent dye (*a contraindication to LAFA does not exclude the patient from other measurements within the study protocol*).
- Patient unable to lie supine and immobile for at least 10 minutes during the imaging procedure.
- End-stage liver disease
- Severe clinical asthma

LAFA Procedural Steps:

1. Each patient is entered into the Novadaq SPY *Elite*[®] computer system, with pre-set optimized settings for appropriate visualization for LAFA.
2. Utilizing a standard protocol per the manufacturer (Novadaq SPY *Elite*[®] system), a 7.5mg (3mL) solution of ICG (reconstituted with sterile saline) is injected intravenously into each patient.
3. The patient is asked to lie supine, immobile for a period of approximately 10 minutes
4. The device is placed over the limb/amputation stump being studied and centered to allow full visualization of the entire stump
 - a. Prop up and immobilize stump
 - b. Obtain a still color image of the stump
 - c. Start an image buffering time of between 10-30 seconds
 - d. ICG is intravenously injected by the patient's nurse or a member of the study team.
 - e. ICG injection is followed by a 10mL of sterile saline flush in the same intravenous line.
 - f. A member of the study team will obtain LAFA imaging of the stump for a total of 150-180 seconds.
 - g. All study images will be stored on the Novadaq SPY *Elite*[®] system hard drive. Study images, including only the study ID and date of exam, will be loaded onto a jump drive and then immediately downloaded onto the WUSTL Department of Surgery/Vascular network drive. The images will then be deleted from the jump drive..
5. Each study patient will be carefully monitored by a physician, nurse practitioner, physician assistant or nurse for signs and symptoms of allergic reaction or intolerance to this non-invasive procedure until discharge.

B. Measurement of Transcutaneous Oxygen Pressure (TcPO₂)

Location of Procedure:

- Barnes-Jewish Hospital Operating Rooms
- 4400/8300/7400/7500 Inpatient Hospital Units
- Other Hospital Units also housing vascular surgery patients

Time of Data Collection:

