- **Day 0 (Day of Operation):** If possible and/or equipment available, obtained prior to the operation at the anticipated level of the amputation.
- **Postoperative Day3:** If possible and/or equipment available, obtained following dressing removal at bedside in the inpatient hospital unit.
- **Postoperative Day5:** If possible and/or equipment available, also obtained at bedside in the inpatient hospital unit if the patient is still in-house.

[figure not shown]
Contraindications to Measurement:

- Patient refusal/inability to participate in measurement before or during data collection
- Patient SpO₂ < 92%, Patient is febrile >38°C, unstable vitals
- Patient unable to lie supine for at least 20 minutes during measurement collection
- Patient unable to breathe normobaric oxygen
- *A contraindication to TcPO₂ measurements does not exclude the patient from other measurements within the study protocol

Protocol Steps:

1. Ensure patient meets the eligibility criteria above.
2. Keep patient covered, and expose the anticipated amputation site or at the amputation stump. Do not elevate the site throughout the measurement collection.
3. Select 4 collection sites as follows:
 1. 3 sites on the anticipated amputation site the stump site, one per section. (Figure 1)
 2. 1 control site on the left anterior chest in indicated on figure. (Figure 1)
4. Electrodes will be placed as per TCM Manual instructions, replicated below with the following specifications:
 1. Temp. set to 45°C.
 2. Do not place probes on scar tissue or dermatologically compromised sites.
 3. Do not place probe over bone.
5. After 15-20 minutes, record the TcPO₂ numbers in all 4 sites. Mark the location of the sites for future measurements to ensure a consistent location for measurement and control (days 2 and 4).
6. Remove probes from patients.

Figure 1

listed

or at

area

Data Analysis:

After TcPO₂ measurements have been collected, the 3 amputation site measurements will be averaged to calculate a mean TcPO₂. The control site measurement on the operated leg will be used to calculate a Regional perfusion index (Mean TcPO₂ / Chest/Control TcPO₂). The non-operated leg measurement site (compared against the operated site) will be used to determine if lower TcPO₂ values in the amputation site are due to regional or systemic oxygenation.

How to place an electrode

Step	Action
------	--------

1. Calibrate the tcpO₂ electrode.

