All AEs will be recorded in the CRF from the time of consent through the 30 days post-operative visit however all AEs will be followed to resolution or stabilization.

Study Outcome Measurements and Ascertainment

As described previously, study subjects will undergo evaluations using LAFA, TcP02, and anthropometric measurements.

Statistical Plan

Sample Size Determination and Power

The purpose of this study is to obtain sufficient preliminary data to determine the sample size necessary for a future large definitive clinical trial. For this pilot study, we plan to enroll 25 patients in each group, allowing for a dropout rate of 10% per group.

We emphasize that effect size (the expected difference in primary outcome between the treatment and control groups) should not be determined by the pilot study. Rather it is determined by the minimum clinically important difference. However, the effect size from the pilot give us some ideas about possible achievable difference.

Interim Monitoring and Early Stopping

An interim analysis will be conducted once >30 patients are enrolled in the study. Analysis will focus on determining differences between NAC and control group. Interim analysis will help determine early differences between the study groups and safety profile of study intervention. The investigators may end the study early depending on study findings, safety profile of the data, and/or if data is adequate for a peer-reviewed publication.

Analysis Plan

Data analysis include (1) the partition of variation of outcome measurements into within and between patient components to obtain standard deviation of measurements, intra-class correlation of the measurements, (2) use of appropriate regression model (GEE or mixed effect regression) to compare the outcome measurements between two groups, while accounting for the intra-class correlation. Interpretation of analysis should be made within the context of a pilot study where we have a pre-specified hypothesis but do not have power analysis for testing the hypothesis.

Statistical Methods

One of the main study outcomes (and in the future large study) is the stump perfusion assessment, which is a continuous variable measured three times (D0, D3, and D5) after

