One of the main study outcomes (and in the future large study) is the stump perfusion assessment, which is a continuous variable measured three times (D0, D3, and D5) after treatment. Based on this longitudinal repeated measurement study design, the preliminary data needed for designing future study include: (1) variance of single measurement, (2) covariance (correlation) among the repeated measurements over time within an individual, (3) level of outcome measurements in patients with and without the treatment.

Missing Outcome Data

Not applicable

Unblinding Procedures

The BJH Investigational Pharmacy will maintain a record of each patient's medical record number and to which arm of the study they were assigned. No member of the vascular surgery investigational team will have access to this information. This will serve to maintain blinding and reduce any unwanted during the trial and subsequent analysis of collected data. Un-blinding of patient data will occur during the interim analysis, and at the end of the study. For un-blinding the pharmacy will then un-blind the study to the investigators such that appropriate conclusions can be made regarding the efficacy of the investigational agent.

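### The pre-dose D0 perfusion reading is labelled as taken after treatment and has no stated baseline role, so the plan leaves open counting it as a treated outcome

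*Combined protocol and SAP*

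**What the plan says.** The SAP (Statistical Methods) calls the stump perfusion assessment one of the main outcomes, "which is a continuous variable measured three times (D0, D3, and D5) after treatment". The protocol's own Statistical Methods section carries the same sentence.

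The protocol's procedures give this timing:

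- **Randomisation** (Randomization Method and Blinding): "Prior to proceeding to the operating room for lower extremity amputation, the patients will be randomized 1:1".
- **D0 LAFA** (Schedule of Measurements, A): "Obtained in the operating room after amputation, but before placement of dressings".
- **First dose** (Treatment Regimen): "The first infusion will be administered within three hours from leaving the operating room".
- **No D0 LAFA** (Early Withdrawal of Subjects): such a patient "will be withdrawn from the study at that time point and will not receive the investigational product".
- **Day 0 TcPO2** (Schedule of Measurements, B): "If possible and/or equipment available, obtained prior to the operation at the anticipated level of the amputation".
- **POD5 LAFA** (Schedule of Measurements, A): "Obtained at the bedside in the inpatient hospital unless the patient is discharged".

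The Analysis Plan names a GEE or mixed-effects model for the group comparison, allowing for intra-class correlation. It mentions no time term, arm-by-time term, change score or baseline covariate. The one study assessment called baseline is the clinical evaluation under Screening for Eligibility, and perfusion is not in its list.

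**The concern.** A reading taken before the first dose cannot carry a drug effect. Because D0 is also free of any systematic arm difference by randomisation, its natural use is as a baseline. The plan instead groups it with the two post-dose readings and then asks for a comparison of the arms. Taken literally, that invites a model with three treated outcomes and one arm effect, which pulls the Aim 1 estimate toward zero.

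The pilot's products are also exposed. Statistical Methods asks for the outcome level with and without treatment, to design the next trial. If the level is averaged over days, the treated level includes undosed readings. The Secondary Aim and the Rationale for the Selection of Outcome Measures both look to this pilot for the effect size of the larger trial. The unblinded interim analysis, which may end the study, also focuses on the difference between arms.

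**Working it through.** **1. Order of events.** Randomisation, then amputation, then D0 LAFA in the operating room, then departure, then first infusion. The rule that a patient without D0 LAFA is not dosed confirms the order. Day 0 TcPO2 comes earlier still. The expected arm difference at D0 is therefore zero on both instruments.

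**2. Could treatment mean the amputation?** That would suit LAFA but not TcPO2, which is pre-operative on Day 0 and which the Design Summary lists among the stump perfusion assessments. The same Statistical Methods paragraph also uses the word for what distinguishes treated from untreated patients.

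**3. The plan's own figures.** 25 + 25 = 50 patients, and 25 × 0.9 = 22.5 evaluable per arm; n = 22 is used below. The plan states no power, alpha, SD, effect size or correlation, so there is no power figure to reproduce.

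**4. Dilution if one arm effect is pooled.** Assumptions: true effects (0, d, d) at D0, D3 and D5; unit SD; exchangeable correlation r; a fraction m of POD5 readings missing at random, equally in both arms. The generalised least squares weights are

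- a = (1−m)/(1+2r) + m/(1+r) on D0 and on D3
- b = (1−m)/(1+2r) on D5

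and the retained share of the true effect is (a+b)/(2a+b). With m = 0, a = b and the share is 2/3 for any r. At r = 0.5:

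| POD5 missing | a | b | Retained share | Undosed share of treated-arm readings, 1/(3−m) |
|---|---|---|---|---|
| 0% | 0.500 | 0.500 | 0.667 | 33% |
| 20% | 0.533 | 0.400 | 0.636 | 36% |
| 40% | 0.567 | 0.300 | 0.605 | 38% |
| 60% | 0.600 | 0.200 | 0.571 | 42% |

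Other correlations change little: at 0/20/40/60% missing, r = 0.3 gives 0.667/0.638/0.608/0.575 and r = 0.7 gives 0.667/0.635/0.602/0.569. If D0 correlates only 0.2 with the later readings (D3–D5 correlation 0.5), the shares are 0.59/0.58/0.56/0.54. Under AR(1) with complete data they run from 0.63 (r = 0.3) to 0.55 (r = 0.8). As a check, 300 simulated exchangeable GEE fits with a true effect of 0.8 SD, 25 per arm and r = 0.5 gave a mean estimate of 0.521, against 0.8 × 2/3 = 0.533 expected.

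**5. Illustrative power.** Assumed: d = 0.5 SD, n = 22 per arm, two-sided 0.05, normal approximation. The adjusted contrasts come from a constrained longitudinal model with a common D0 mean. Complete data, r = 0.5:

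- Pooled: estimate 0.333; variance (2/22)(1+2r)/3 = 0.0606, SE 0.246; power Φ(1.354 − 1.96) = 0.27.
- Adjusted POD5: variance (2/22)(1−r²) = 0.0682, SE 0.261; power Φ(1.915 − 1.96) = 0.48.
- Adjusted D3/D5 mean: variance (2/22)[(1+r)/2 − r²] = 0.0455, SE 0.213; power Φ(2.345 − 1.96) = 0.65.

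With missing POD5 readings, the pooled variance is 2/[22(2a+b)]. The adjusted contrasts use the inverse of the information matrix for the D3 and D5 effects. At r = 0.5 and m = 0.4 that matrix, before the factor 22/2, is [1.433, −0.3; −0.3, 0.9], with determinant 1.2. The D5 variance is (2/22)(1.433/1.2) = 0.109 (power 0.33), and the variance of the mean is (2/22)(1.194 + 0.75 + 2 × 0.25)/4 = 0.056 (power 0.56).

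| Power at 0 / 40 / 60% POD5 missing | r = 0.3 | r = 0.5 | r = 0.7 |
|---|---|---|---|
| Pooled, D0 as outcome | 0.33 / 0.26 / 0.23 | 0.27 / 0.22 / 0.20 | 0.24 / 0.20 / 0.18 |
| Adjusted POD5 | 0.41 / 0.28 / 0.20 | 0.48 / 0.33 / 0.24 | 0.64 / 0.46 / 0.34 |
| Adjusted D3/D5 mean | 0.60 / 0.51 / 0.42 | 0.65 / 0.56 / 0.48 | 0.79 / 0.71 / 0.63 |

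The power advantage of adjusted POD5 over pooling is gone at about 45% missing for r = 0.3 and about 71% for r = 0.5. The D3/D5 mean keeps its advantage throughout.

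**The case against.** The strongest reply is that dilution depends on a model the plan never specifies. The SAP calls the design longitudinal and wants correlations over time, and Aim 1 speaks of perfusion by POD 5. A model with time and arm-by-time terms fits the text at least as well and has no dilution. Anyone holding the schedule would see that D0 is pre-dose. The power figures rest entirely on assumed inputs, in a pilot that disclaims power. The SAP also says that effect size should come from the minimum clinically important difference, and variances and correlations can still be estimated by time point.

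Most of this stands, and it limits the weight of the point: the dilution is conditional, the power figures show direction only, and the consequence for the next trial is modest. It does not remove the point. The sentence is wrong about D0, and nothing elsewhere corrects it or requires the harmless model. The SAP still takes an indication of the achievable difference from the pilot effect.

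Nor does an arm-by-time model alone recover everything. Without D0 adjustment or a common D0 mean, POD5 power is 0.38 rather than 0.48 (r = 0.5, complete data: variance 2/22, SE 0.302, Φ(1.658 − 1.96)). It is also fair to note that Day 0 TcPO2 is measured on the limb before amputation, not on the stump. Its expected arm difference is still zero, so it is a valid baseline, but its role should be described separately from that of LAFA.

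**Conclusion.** The concern holds. D0 is a pre-dose reading on both instruments, is described as post-treatment in both statistical sections, and has no stated baseline role. That much rests on the text alone.

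The consequence is conditional. It is zero dilution under an arm-by-time or D0-adjusted model. If one arm effect is pooled over the three readings, the estimate keeps about two-thirds of the true effect with complete data and 0.57 with 60% of POD5 missing, assuming equal effects at D3 and D5 and exchangeable correlation 0.5. The retained share falls to about 0.55 under the other correlation patterns tried. This should be fixed before analysis, but it does not undermine the design.

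**What to change.** In both Statistical Methods sections, state that perfusion is measured once before the first dose (D0, baseline) and twice after it (D3 and D5). Then specify:

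- **Model.** Compare arms on D3 and D5 with arm, time and arm-by-time terms, adjusting for D0, or use a constrained longitudinal model with a common D0 mean. For TcPO2 use the constrained form, because the Day 0 reading is optional and patients without it would otherwise be dropped. Say that this reading comes from the limb before amputation.
- **Contrast.** State in advance whether the D3/D5 mean or POD5 answers Aim 1, and report the other beside it. The Aim 1 wording fits either.
- **Design inputs.** Report levels and variances by time point, and the D0–D3, D0–D5 and D3–D5 correlations separately.

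The cost is one sentence in two places and a short model specification, with no new data and no extra patients. The choice of contrast carries a trade-off. POD5 alone loses power when discharged patients have no reading (0.33 against 0.56 for the mean at r = 0.5 with 40% missing). If D3 carries only 60% of the D5 effect, the mean has no gain with complete data (0.47 against 0.48) and a smaller one with 40% missing (0.40 against 0.33). Either choice is defensible; it needs to be stated.

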In this pilot clinical study we propose to conduct a prospective, randomized, double-blinded, placebo-controlled clinical trial for 30 days for patients with CLI who undergo a major (above-knee or below-knee) lower extremity amputation. By exploring the primary endpoints we aim to

determine whether NAC can affect amputation stump perfusion and healing. Based on our preclinical data, we hypothesize that NAC will augment both amputation stump perfusion as well as healing. We will utilize the data from this trial to determine the true effect size that is necessary for a larger clinical trial to determine the clinical efficacy of NAC in healing surgical sites such as major lower extremity amputation stumps.

In addition, we will obtain MR perfusion studies on 6 subjects (3 NAC and 3 placebo) conducted at approximately post-operative day (POD) 4. The study team will continue to remain blinded to their study drug randomization. The study pharmacist will notify the study team of which subjects will be eligible to have an MR perfusion study. For example, if the MR perfusion portion of the study has already recruited 3 patients from the NAC group, and the fourth eligible patient also randomizes to NAC, the pharmacy will notify the study team that the patient is not eligible for the MR perfusion study.

MR perfusion studies will be performed by [name] and his research on a Siemens Prisma 3.0 T MR (Software version VE11c (latest software version), 40 mT/meter; 200 μ sec rise time) in CCIR. The subject will lie down on a MRI table and The MRI scan will undergo only at rest. The MR study will be performed without using of any MR contrast media. The scan protocol will involve scout imaging to localize the calf and stump regions. This will be followed by perfusion, diffusion, and oxygenation imaging in these regions. The expected scan time will be less than 45 min.

MR perfusion studies will only be used for research purposes (i.e. will not direct medical/clinical therapy). MR perfusion will be used to assess skeletal muscle perfusion at the healing amputation stump. This data will be used in adjunct to assess overall stump perfusion along with the LAFA studies that are will already be performed on the patient.

Investigational Agent

Preclinical Data

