 23. Kapp, M.B., *Ethical and legal issues in research involving human subjects: do you want a piece of me?* J Clin Pathol, 2006. **59**(4): p. 335-9.
 24. Holdiness, M.R., *Clinical pharmacokinetics of N-acetylcysteine.* Clin Pharmacokinet, 1991. **20**(2): p. 123-34.

STATISTICAL ANALYSIS PLAN

**Protocol Title: N-Acetyl-Cysteine for Healing of
Amputation Stumps in the Setting of Diabetes**

NCT03253328

**Protocol Version 11.0
Date: March 26, 2020**

Statistical Plan

Sample Size Determination and Power

The purpose of this study is to obtain sufficient preliminary data to determine the sample size necessary for a future large definitive clinical trial. For this pilot study, we plan to enroll 25 patients in each group, allowing for a dropout rate of 10% per group.

We emphasize that effect size (the expected difference in primary outcome between the treatment and control groups) should not be determined by the pilot study. Rather it is determined by the minimum clinically important difference. However, the effect size from the pilot give us some ideas about possible achievable difference.

Interim Monitoring and Early Stopping

An interim analysis will be conducted once >30 patients are enrolled in the study. Analysis will focus on determining differences between NAC and control group. Interim analysis will help determine early differences between the study groups and safety profile of study intervention. The investigators may end the study early depending on study findings, safety profile of the data, and/or if data is adequate for a peer-reviewed publication.

Analysis Plan

Data analysis include (1) the partition of variation of outcome measurements into within and between patient components to obtain standard deviation of measurements, intra-class correlation of the measurements, (2) use of appropriate regression model (GEE or mixed effect regression) to compare the outcome measurements between two groups, while accounting for the intra-class correlation. Interpretation of analysis should be made within the context of a pilot study where we have a pre-specified hypothesis but do not have power analysis for testing the hypothesis.

Statistical Methods

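### The randomization section withholds allocations from the team until the trial ends, but the unblinding section releases them to the investigators at the interim, where early stopping has no stated criterion.

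*Combined protocol and SAP*

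**What the plan says.** On who sees allocations:

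- Protocol, Randomization Method and Blinding: the pharmacy keeps the blind, "with no member of the investigational team having access to the record until the conclusion of the trial".
- Protocol and SAP, Unblinding Procedures (same text in both): "No member of the vascular surgery investigational team will have access to this information". Two sentences later: "Un-blinding of patient data will occur during the interim analysis, and at the end of the study". The section ends by saying that "the pharmacy will then un-blind the study to the investigators such that appropriate conclusions can be made regarding the efficacy of the investigational agent".

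On the interim (Interim Monitoring and Early Stopping, same text in both): the look takes place once more than 30 patients are enrolled. It compares NAC with control and reviews safety. The investigators "may end the study early depending on study findings, safety profile of the data, and/or if data is adequate for a peer-reviewed publication".

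The design summary gives two primary endpoints, stump healing and stump perfusion. Visit 1, where the stump is assessed after discharge, falls 20-50 days after discharge. The principal investigator is the medical monitor and decides on stopping for safety (Medical Monitoring; Study Monitoring Plan). Committees is marked as not applicable.

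**The concern.** The two blinding rules differ on the one date that matters before the end of the trial. When the interim arrives, the pharmacy must either withhold the allocations, as the randomization section requires, or release them, as the unblinding section requires.

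Release matters because judgement-based assessment continues after the look. The protocol refers to a stump healing score and a qualitative perfusion reading, the study team acquires the fluorescence images, and the investigator classifies adverse events. Investigators who know earlier allocations and results would make these assessments for later patients. For patients already enrolled but still awaiting Visit 1, they could know the patient's own arm.

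The secondary question is what the same unblinded investigators may do with the result. Two of the three stopping grounds, findings and readiness to publish, have no outcome, time point, threshold or fixed look size. The pilot is meant to supply the variance, the within-patient correlation and the outcome levels for a larger trial. How far an early stop harms these depends on why the trial stops.

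**Working it through.** **1. The texts side by side.** At the interim, the randomization section gives the team no access, because the trial has not concluded. The unblinding section gives the investigators access, because the interim is one of its two listed occasions. It refers to patient data, sets no limit to group-level results and names no separate analyst. No other section resolves the difference.

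**2. Patients affected.** Inputs: 25 per group, so 2 × 25 = 50 (design summary and sample-size section agree); earliest look at 31 enrolled.

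- Enrolled after the look: 50 − 31 = 19, or 19/50 = 38%. This is an upper limit, since the look may come later or the trial may stop.
- Earlier patients unblinded before Visit 1: this depends on accrual, which is not stated. Assume 1-4 enrolled a month, discharge about day 5 and unblinding on the day the 31st enrols. The interval from enrolment to Visit 1 is then 5 + 20 = 25 to 5 + 50 = 55 days. Rate × days / 30.4 gives 1 × 25 / 30.4 = 0.8 to 4 × 55 / 30.4 = 7.2. With even spacing and the 31st patient counted, that is 1 to 8. It is none if the look waits for their Visit 1.

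**3. Precision if the trial stops early.** The 95% half-width for a difference, in SD units, is t(0.975, df) × √(1/a + 1/b):

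- 25 and 25 patients, df 48: 0.57
- 20 and 20, df 38: 0.64
- 16 and 15, df 29: 0.74

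The upper 95% limit for the variance, as a multiple of its estimate, is df / χ²(0.025, df): 1.56 at df 48 and 1.81 at df 29. A future sample size is proportional to this variance.

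**4. Bias under assumed stopping rules.** The plan states no rule, so these are illustrations. Setting: 400,000 simulated trials, normal data, SD 1, true difference 0.3 SD, look at 16 and 15 patients (t-test, 29 df), otherwise continue to 25 and 25.

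| Assumed rule | Trials stopped | Mean estimate if stopped | Mean over all trials |
|---|---|---|---|
| Benefit, two-sided p < 0.05 | 12.5% | 0.87 | 0.33 |
| Any unfavourable difference | 20% | −0.20 | 0.26 |
| Either | 33% | 0.21 | 0.29 |
| Always stop at 31 | 100% | 0.30 | 0.30 |

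The mean estimated SD over all trials falls by only 0.2-0.6%, so bias in the SD is negligible.

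**The case against.** **The unblinding section does not clearly contradict itself.** A reader might infer that it does, since it denies the team access and then grants it. But it can be read as a rule followed by its exceptions. Taken literally, the no-access sentence would also bar unblinding at the end of the study. That tension is only supporting evidence; the firm conflict is with the randomization section, whose end-of-trial limit leaves no room for an interim exception. Two other blinding statements are also weak support: "The study team will continue to remain blinded to their study drug randomization" concerns the six MR subjects, and "study drug will be blinded to the research team and the study participant" concerns dispensing.

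**Only group-level results may be meant.** This is possible, but the text does not say so.

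**Biased assessment is not established.** A reader might infer that outcomes will be biased. The documents show an opportunity for bias, not its occurrence. Nor does the text release the arms of patients enrolled after the look before the end of the study; for them the route is knowledge of earlier allocations and results.

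**This is a pilot.** It disclaims a power analysis and states no alpha. A reader might infer an inflated type I error: testing at an assumed two-sided 0.05 at 31 and again at 50 would give 0.079. With no test level in the plan, that is illustration only. Nor can one say that the estimates are unreliable in general. Under the assumed rules the mean over all trials is 0.26-0.33 against a true 0.30, which is small beside a half-width of 0.57 SD. The large figure, 0.87, arises in one trial in eight under one assumed rule.

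**The precision loss is not certain.** The investigators may stop; they need not. Any early stop, including one for safety, has the same cost. This objection stands.

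**Conclusion.** The concern holds as a conflict between the protocol's Randomization Method and Blinding section and the Unblinding Procedures section of both documents. It rests on the wording alone, needs no assumed figure, and must be resolved before the interim.

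The stopping rule is a lesser point. The missing outcome, threshold and look size are a real gap, but the consequence depends on the reason for stopping. A stop because enough data have accrued, regardless of the result, biases nothing and costs precision. A stop because the interim looks favourable overstates the effect in the trials that stop, which matters to the extent that the Secondary Aim's effect size is carried forward. The bias figures assume normal data, a true difference of 0.3 SD, a look at 31 and stopping rules that the plan does not contain.

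**What to change.** 1. **Blinding.** In Unblinding Procedures (protocol and SAP), remove the interim as an occasion for unblinding, so that investigators receive patient-level allocations only at the end, in agreement with the randomization section.
2. **Interim text.** In Interim Monitoring and Early Stopping (both documents), delete findings and readiness for publication as reasons to stop. Also delete, or restrict to safety, the two sentences that direct the interim at differences between the groups. Otherwise an arm comparison is still required and nobody is authorised to hold the allocations for it.
3. **Safety.** Keep safety as a reason to stop and leave the principal investigator's safety role in place. State who prepares any by-arm safety summary without passing patient-level allocations to outcome assessors, and how a safety concern reaches the principal investigator.
4. **Only if an efficacy look is kept.** Name the endpoint, look size and boundary in advance, hold the look after the included patients complete Visit 1, and have it run by someone outside the outcome-assessing team.

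Cost: wording changes, with no added patients or visits. The investigators lose the discretion to stop early on efficacy or for publication. A by-arm safety summary or an efficacy look would need a person whom the documents do not currently name.
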